6.3.3 Assessment of Safety Endpoints

AEs, including Serious Adverse Events (SAEs) will be graded according to severity using the Consortium of Food Allergy Research (CoFAR) scale, which is 5-point ordered scale from mild (1) to death (5). AEs will be categorized by preferred term using the Common Terminology Criteria for Adverse Events (CTCAE) Version 5.0 and for the specific AEs for interest listed in section 5.2, by treatment required, and by study phase (dose escalation study visits, home doses, exit DBPCFC, and overall).

7 Sample Size

We will compare with proportion of patients successfully desensitized as defined by meeting the primary endpoint with the expected placebo rate. The null hypothesis is that the proportion of patients successfully desensitized by boiled peanut oral immunotherapy will not be greater than the expected 20% that has been previously published as the proportion of patients successfully meeting the primary endpoint in OIT studies (which aligns with the expected 20% that would naturally “outgrow” a peanut allergy). If we reject this null hypothesis, we will be able to conclude that the proportion of successfully desensitized by boiled peanut therapy is greater than placebo. The sample of 10 patients will provide >90% power to determine the expected success rate (80%) is greater than a theoretical placebo rate (20%).

8 General Analysis Considerations

8.1 Timing of Analyses

No interim analyses are planned. The final analysis will be performed on data transferred to the study statistician, having been documented as meeting the cleaning and approval requirements of the study protocol and after the finalization and approval of this SAP document.

8.2 Analysis Populations

8.2.1 Primary Endpoint Intention to Treat (ITT) Population

- *All patients enrolled in study following the initial OFC.*

8.2.2 Efficacy Population

- *All patients who completed both initial OFC and exit DBPCFC.*

8.2.2.1 Modified Efficacy Population for Immune Response

- *Patients with serum testing for at least one peanut-specific marker of sensitization and tolerance at both the initial dose escalation visit and exit DBPCFC.*

8.2.2.2 Modified Efficacy Population for FAQLQ-PF

- *Patients with at least one subscale or summary score at both enrollment/baseline and exit DBPCFC, on the same FAQLQ age-group-specific parent form.*

8.2.2.3 Modified Efficacy Population for FAQLQ-TF

- *Patients with at least one subscale or summary score on the FAQLQ teenager form at both enrollment/baseline and exit DBPCFC.*

8.2.3 Safety Population

- *All enrolled patients who took at least one dose of study medication during any dose escalation visit or at home, or participated in either arm of the exit DBPCFC.*

8.2.4 Study Visit Populations

- *For each SV, all patients with a documented date of visit.*

8.3 Covariates and Subgroups

No subgroup analyses are planned.

8.4 Missing Data

With the exception of the primary endpoint, missing data will not be imputed and analyses will be performed on a complete-case basis, due to the small sample size and exploratory nature of the study. The expected sample size is smaller than is practical to analyze under multiple imputation, with little ability to assess the missing at random assumption. A carry-forward approach is likely to be too conservative to provide useful information for future study planning or hypothesis generation. Patients with missing data on particular endpoints will be excluded only for analyses in which those variables were used, and the results of the complete-case analyses will be interpreted as pertaining to patients with data on the specific analyzed endpoint. Sample sizes will be noted for all descriptive statistics and analyses.

8.5 Multiple Testing

As this is a proof-of-concept study with a single primary endpoint, no adjustment for multiple testing will be performed. The use of hypothesis testing is limited to primary and secondary efficacy endpoints, and within the FAQLQ analysis, to total scores only. Detailed descriptive statistics will be presented for secondary endpoints, along with unadjusted p-values, and reports will interpret hypothesis testing for secondary endpoints as hypothesis-generating rather than confirmatory.

9 Summary of Study Data

Continuous variables will be summarized using the following descriptive statistics: n (non-missing sample size), median, 25th and 75th percentiles, maximum, and minimum (range). Categorical variables will be summarized with the frequency and percentages (calculated using the non-missing sample size as the denominator) of observed levels. All summary tables will list the total analysis population and missing data for the table, and for individual variables in the table where different from the total. Data listings will be sorted by subject and, where necessary, by visit number within subject.

Because the secondary efficacy analyses of changes in highest tolerated dose and cumulative dose of peanut protein, serum markers of sensitization and tolerance to peanut, and FAQLQ scores will be performed on a complete-case basis, the sample sizes of non-missing data for the initial and final values may be larger than the sample sizes of non-missing data for the change variables. Therefore additional descriptive tables will present univariable summary statistics for all non-missing data for the initial and final values of these variables. (Refer to mock Tables 4.3-4.6.)

9.1 Subject Disposition

All subjects in the study database will be considered as assessed for eligibility. Subject disposition will be described based on the database fields on the case report forms (CRFs) 'Inclusion/Exclusion BPOIT', 'Demographics' (field indicating date of signed consent), 'Oral Food Challenge' (field indicating date of participation), 'Study drug administration' (any dose of study medication administered indicates enrollment in study), 'Off study/continued therapy' (field indicating the reason the patient came off the study). (Refer to mock Table 1.1.)

9.2 Derived variables

9.2.1 Derivation of Primary Efficacy Endpoint

The primary efficacy endpoint is 'response to treatment' at the exit DBPCFC. A subject will be defined to have response to treatment if the question, 'Was 300mg dose tolerated' on the CRF corresponding to the peanut protein arm of the DBPCFC was marked 'Yes'. If this question is marked 'No', or the subject did not complete the DBFCFC for any reason, the subject will be defined as no response to treatment.

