Though immunotherapy can be administered in a variety of methods, oral immunotherapy (OIT) has shown the most promise in the treatment of food allergy. Several recent trials have utilized the technique of oral immunotherapy for treatment of peanut and other food allergies. This therapy involves mixing the food allergen into a vehicle of choice and having the subject begin daily consumption while gradually increasing the dose. Several endpoints have been defined when evaluating the response to immunotherapy. Desensitization results in a higher threshold for an allergic reaction, typically above the amount that will be encountered in an accidental exposure. However, this does require ongoing dosing. The most desirable outcome of OIT is sustained unresponsiveness, or continued long term tolerance of the food without the need for daily maintenance therapy.

Although individual responses vary considerably, OIT will induce significant desensitization in most subjects who are able to tolerate the therapy. However, these studies are limited by frequent treatment related AEs and high rates of withdrawal due to these AEs. The reported AEs and dropout rates from representative studies are outlined in Table 1.⁸⁻¹⁶

There is a large amount of heterogeneity in the reporting of AEs. More specifically, AEs are at times reported in terms of the percent of subjects experiencing an adverse reaction. At other times, adverse reactions are reported in terms of the percent of doses that cause an AE. This method is often utilized to report AEs during maintenance dosing. This is in part due to the fact that over the course of all phases of an individual study and when including mild AEs in addition to more significant reactions, nearly 100% of patients have some form of AE during treatment. Thus it may be more meaningful to report the percent of doses causing symptoms at times.

Table 1: Prior OIT Trials

Author	N	Age	Design	Adverse Events	Drop outs	Additional Detail on Drop Outs
Jones et al 2009 [8]	39	1-16	Open label	92% of subjects on initial escalation day, 46% doses during build up, 3.7% doses during maintenance	10 (25%)	4 withdrew for allergic effects and 6 for personal reasons
Hofmann et al 2009 [10]	28	1-16	Open label	93% of subjects on initial escalation day, 46% doses during build up, 3.5% of doses during maintenance	5 (18%)	3 withdrew following initial escalation, 1 during build up, 1 during maintenance

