6.1.2 Dosing and Administration

Oral Food Challenge

After informed consent is obtained (and assent when relevant), eligible subjects will undergo an open roasted peanut graded food challenge to 4000 mg of peanut protein to confirm peanut allergy and to determine the amount of peanut protein required to induce an allergic reaction at baseline. An oral food challenge is the gold standard for diagnosis of food allergy. PB2 peanut powder (PB2 Foods, Tifton, GA) will be used exclusively for this challenge, mixed in a vehicle of the family's choice (such as applesauce, pudding, etc.).

Subjects will be instructed to hold medications with strong antihistamine properties for five days prior to the challenge (diphenhydramine, loratadine, desloratadine, cetirizine, levocetirizine, fexofenadine, azelastine). The challenge will not be performed in the setting of acute illness, including febrile illness, asthma exacerbations, and significant flares of atopic dermatitis.

The oral food challenge protocol is outlined in Table 3. The initial oral food challenge will take place under the supervision of a trained Allergy/Immunology investigator and trained Allergy/Immunology nurse at Cleveland Clinic Children's main campus Allergy Clinic, where similar food challenges are routinely conducted. The physician investigator available will be trained in recognition and treatment of IgE mediated food reactions, will be available for immediate evaluation of any signs or symptoms of reaction.

Table 3: Oral food challenge to peanut for enrollment (Study Visit 1)

Time	Dose	Clinician Intervention *
0	5mg	Obtain weight, temperature, heart rate, blood pressure, respiratory rate, and oxygen saturation level. Peak flow will be done on patients 4+ or deemed developmentally appropriate. Full physical examination of ears, oropharynx and nose, lungs, and skin prior to administration of dose
+15 minutes	10mg	Examination of skin and auscultation of lungs prior to dose
+30 minutes	25mg	Examination of skin and auscultation of lungs prior to dose
+45 minutes	50mg	Examination of skin and auscultation of lungs prior to dose
+60 minutes	100mg	Examination of skin and auscultation of lungs prior to dose
+75 minutes	500mg	Examination of skin and auscultation of lungs prior to dose
+90 minutes	1000mg	Examination of skin and auscultation of lungs prior to dose

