+105 minutes	4000mg	Examination of skin and auscultation of lungs prior to dose Full physical examination of ears, oropharynx and nose, lungs, and skin after completion of final dose.

*Vital signs including heart rate, blood pressure, respiratory rate and oxygen saturation level to be obtained with any change in physical exam or clinical status

If objective signs of an allergic reaction occur, then the challenge will be stopped, and the subject treated based on the presenting symptoms and clinical judgment of the supervising investigator (Table 4). If no objective signs occur within 2 hours after the last dose is consumed, then the child will be considered not peanut allergic and will not qualify for the study.

Table 4: Oral food challenge stopping criteria

A positive food challenge will be defined by the presence of either of the following:
 
 • One or more major criteria • Two or more minor criteria 
An indeterminate food challenge will be defined by the presence of one minor criterion.
 
A negative food challenge will be defined by the absence of major or minor criteria.
 
All symptoms should be of new onset and not due to ongoing disease. Symptoms must occur no later than 2 hours after the last dose.

Major Criteria

 • Confluent erythematous pruritic rash • Respiratory signs (at least one of the following): 
 Wheezing Inability to speak Stridor Dysphonia Aphonia • $>/= 3$ noncontact urticarial lesions lasting for more than 3 minutes • $>/= 1$ site of angioedema • Hypotension for age not associated with vasovagal episode • Evidence of severe abdominal pain (such as abnormal stillness or doubling over) that persists for more than 3 minutes
Minor Criteria

 • Vomiting (persistent symptoms would elevate to major criterion) • Diarrhea • Persistent rubbing of nose or eyes that lasts for $>/= 3$ minutes • Persistent rhinorrhea that lasts for $>/= 3$ minutes • Persistent scratching that lasts for $>/= 3$ minutes

The subjects with objective signs of an IgE mediated reaction to peanut using standard criteria (Table 4) will be eligible for enrollment.

If patient is found to be study eligible, then a urine pregnancy test will be done on females who have reached the age of child birthing potential.

Initial Dose Escalation

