If a subject does not tolerate a dose increase, then the patient will be administered a dose reduced by 25%, with increase to the originally intended dose at the subsequent visit. If the patient still does not tolerate the dose, then the decision on how to proceed will be determined at the investigator's discretion. This may involve temporarily decreasing the subject's dose, making a smaller increase, or prolonging the duration of a given dose. If any subject is unable to reach the goal maintenance dose, then the investigator may decide to continue the subject on a lower maintenance dose for the duration of the study.

Table 6: Dose Escalation Schedule

Dose of Peanut Protein	Week of Protocol
6 mg	0
12 mg	2
25 mg	4
50 mg	6
75 mg	8
150 mg	10
300 mg	12

Home Dosing

All subjects will be offered the opportunity to continue once daily consumption of the maintenance dose after the end of their study participation. This ongoing maintenance therapy is optional and will not be paid for by the study. The subjects will be instructed to otherwise continue a peanut free diet.

Follow Up

The subject will also undergo a final oral food challenge at the final visit (SV10). This food challenge will be double blind and placebo controlled. A double blind placebo controlled food challenge (DBPCFC) is the gold standard for diagnosis of food allergy and is the standard utilized for most oral immunotherapy trials at exit.

Roasted peanut powder will be utilized for the challenge, with oat flour as placebo. An individual will undergo a standard challenge described below (Table 7) with either the roasted peanut or the placebo, blinded to both subject and investigators. The same individual will then undergo a second challenge with the opposite (either peanut or placebo) either later that day or by returning to clinic the following day. Each challenge will be performed by increasing doses up to a final dose of 1000 mg of peanut protein. The individual doses will be 25, 100, 200, 300, 600, and 1000 mg of peanut protein. The highest tolerated dose will be recorded. If a patient reacted to a dose lower than 25 mg of peanut powder during the initial Oral Food Challenge then they will be started at the dose lower than where the reaction occurred for the DBOFC.

A urine pregnancy test will be repeated on all females of child bearing potential before the DBOFC.

Table 7: Double blind oral food challenge to peanut or control oat (SV 10)

Time	Dose	Clinician Intervention *

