9.1 Statistical Hypothesis

We will obtain observation data on patients receiving boiled peanut oral immunotherapy which has not yet been well described in human trials. We will compare with proportion of patients successfully desensitized as defined by meeting the primary endpoint with the expected placebo rate. The null hypothesis is that the proportion of patients successfully desensitized by boiled peanut oral immunotherapy will not be greater than the expected 20% that has been previously published as the proportion of patients successfully meeting the primary endpoint in OIT studies (which aligns with the expected 20% that would naturally "outgrow" a peanut allergy). If we reject this null hypothesis, we will be able to conclude that the proportion of successfully desensitized by boiled peanut therapy is greater than placebo. For the safety aspect of the study we will be comparing the historical SAEs/AEs of patients who received OIT with roasted peanuts and compare them with the patients enrolled in this study for the rate of occurrence and severity of the SAEs/AEs observed.

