6.3.2 Assessment of Secondary Efficacy Endpoints

Highest tolerated dose and cumulative dose. The highest dose of roasted peanut protein tolerated by the subject, cumulative total dose of roasted peanut protein tolerated by the subject, and the changes in highest tolerated dose and cumulative tolerated dose from initial OFC to the peanut protein arm of the exit DBPCFC will be analyzed as ordinal variables because of the interval nature of the dosing schedule (Chinchilli et al., 2005). The dose schedule for initial OFC and exit DBPCFC is shown below.

Peanut protein challenge dose schedule at initial (SV 1) and exit (SV 10) oral food challenges.

Oral food challenge	Highest tolerated dose of peanut protein (mg)	Cumulative tolerated dose of peanut protein (mg) at initial OFC	Cumulative tolerated dose of peanut protein (mg) at exit DBPCFC
Initial only	5	5	
Initial only	10	15	
Initial and Exit	25	40	25
Initial only	50	90	
Initial and Exit	100	190	125
Exit only	200		325
Exit only	300		625
Initial only	500	690	
Exit only	600		1225
Initial and Exit	1000	1690	2225
Initial only	4000	5690	

Serum markers of sensitization and tolerance to peanut. Changes in serum markers of sensitization and tolerance to peanut from initial dose escalation visit to final study visit will be analyzed as continuous variables.

Food Allergy Quality of Life Questionnaires (FAQQLQ). The Food Allergy Quality of Life Questionnaire – Parent Form (FAQQLQ-PF) will be used for patients aged 0-12 years (DunnGalvin et al., 2008). The Food Allergy Quality of Life Questionnaire –Teenager Form (FAQQLQ-TF) will be used for patients aged 13-17 year (Flokstra-de Blok et al., 2008). For all FAQQLQ surveys, all questions are scored on an ordered scale from 1 (“no impairment”) to 7 (“maximal impairment”) for calculations. Subscale and summary scores are calculated as item mean scores, on the same scale from 1 to 7. Subscale and summary scores, and changes in subscale and summary scores from enrollment/baseline visit to final study visit, will be analyzed as continuous variables. The MID (minimally important difference) for the FAQQLQ is 0.5 (DunnGalvin et al., 2010), and the change in total score will be dichotomized as greater than or equal to 0.5 or less than 0.5 and analyzed as a binary variable. Scoring of the FAQQLQ is detailed in section 9.3.2.

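### The absolute 300 mg exit endpoint, with no ceiling on the baseline reacting dose, can count a child as desensitized with no rise in threshold; a supportive estimate in SAP 10.1 would show whether this matters

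*SAP*

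**What the plan says.** **Endpoint.** SAP 9.2.1: "A subject will be defined to have response to treatment if the question" on whether 300 mg was tolerated, on the peanut-arm form of the exit challenge, is marked yes. A no, or an exit challenge not completed, is non-response. Protocol 3 and SAP 6.3.1 and 10.1 define the endpoint in the same absolute way.

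**Entry.** Protocol 6.1.2 states that children "will undergo an open roasted peanut graded food challenge to 4000 mg of peanut protein", in steps of 5, 10, 25, 50, 100, 500, 1000 and 4000 mg. It then states: "The subjects with objective signs of an IgE mediated reaction to peanut using standard criteria (Table 4) will be eligible for enrollment". The eligibility lists in Protocol 5.1 and 5.2 and SAP 6.2 set no upper limit on the dose tolerated or reacted to. SAP 8.2.1 defines the primary population as "All patients enrolled in study following the initial OFC".

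**Exit.** The steps are 25, 100, 200, 300, 600 and 1000 mg: "Each challenge will be performed by increasing doses up to a final dose of 1000 mg of peanut protein".

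**Inference.** Protocol 9.1 and SAP 7 say that if the 20% null is rejected, "we will be able to conclude that the proportion of successfully desensitized by boiled peanut therapy is greater than placebo". Protocol 2.2 describes the concept as follows: "Desensitization results in a higher threshold for an allergic reaction". That sentence goes on to say that the threshold is typically above an accidental exposure.

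**Change from baseline.** The rise in tolerated dose appears under the primary endpoint heading in Protocol 3 and SAP 5.2, but is analysed as a secondary endpoint in completers (SAP 6.3.2, 8.2.2, 10.2). SAP 8.3 plans no subgroup analyses.

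**The concern.** A child who first reacts at 1000 mg enters having tolerated 500 mg; one who first reacts at 4000 mg enters having tolerated 1000 mg. Either can pass the exit 300 mg step without any treatment effect. In a single-arm trial judged against a fixed 20%, no concurrent control group absorbs such children. The success rule needs only 5 of 10 responders, so one or two of them could decide a borderline result. At stake is the interpretation: whether passing the primary test supports a statement about desensitization beyond placebo.

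**Working it through.** **1. The plan's own figure.** Inputs: n = 10, null 20%, expected 80% (Protocol 9.2, SAP 7); one-sided 0.05, exact binomial and Clopper-Pearson (SAP 10.1).
- P(X ≥ 4 | 0.2) = 0.121 and P(X ≥ 5 | 0.2) = 0.0328, so success needs 5/10.
- The one-sided 95% lower bound is 22.2% at 5/10 and 15.0% at 4/10, which gives the same rule.
- Power = P(X ≥ 5 | 0.8) = 0.994. The stated power above 90% is reproduced.

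**2. Can the case arise?** SAP 6.3.2 sets the two ladders side by side ("The dose schedule for initial OFC and exit DBPCFC is shown below").
- A child who tolerated 500 mg at baseline had taken 5+10+25+50+100+500 = 690 mg. One who tolerated 1000 mg had taken 1690 mg. The exit ladder through 300 mg totals 25+100+200+300 = 625 mg.
- Baseline 500 mg, exit 300 mg: a responder, with change 300 − 500 = −200 mg.
- Baseline 1000 mg: the best exit result is 1000 mg, change 0. No rise can be shown from that baseline.

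**3. Effect on the chance of reaching 5/10.** Let k be the number of enrolled children at 500 or 1000 mg at baseline. The documents do not give k; I show 1 to 3. With all k passing and the others responding at rate p, P(success) = P(Bin(10−k, p) ≥ 5−k). In the third row, each of the k passes with an assumed probability of 80%.

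| Assumption | k=1 | k=2 | k=3 |
|---|---|---|---|
| 20% already includes such children; all k pass; others at (2−k)/(10−k) | 1.2% | 0% | not possible |
| 20% excludes them; all k pass; others at 20% | 8.6% | 20.3% | 42.3% |
| 20% excludes them; each of the k passes with 80%; others at 20% | 7.2% | 14.8% | 27.7% |

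The planned test has 3.3%. In the first row, k=1 leaves 1/9 = 11.1% for the others and k=2 leaves 0%. Three certain responders already exceed 20% of 10. In the second row the mean response is (k + 0.2(10−k))/10 = 28%, 36%, 44%, so the null of 20% or less is false there.

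**4. Effect on the reading of an observed result.** Remove the k baseline-tolerant responders and take the one-sided 95% lower bound among the rest.

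| Total | k=1 | k=2 | k=3 |
|---|---|---|---|
| 5/10 | 4/9: 16.9% | 3/8: 11.1% | 2/7: 5.3% |
| 6/10 | 5/9: 25.1% | 4/8: 19.3% | 3/7: 12.9% |
| 7/10 | 6/9: 34.5% | 5/8: 28.9% | 4/7: 22.5% |
| 8/10 | 7/9: 45.0% | 6/8: 40.0% | 5/7: 34.1% |

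The bound falls to 20% or below only at 5/10 (any k) and at 6/10 (k = 2 or 3).

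**The case against.** - **The SAP derivation is not in error.** This stands. The endpoint is absolute wherever it is defined, and SAP 9.2.1 implements it. Protocol 4.3 supports 300 mg as likely to exceed an accidental exposure, so an absolute threshold is a defensible choice. The gap comes from combining it with open-ended entry.
- **The 20% may already include such children.** Protocol 9.1 presents it as a published rate of meeting the endpoint, in line with natural outgrowing, which reads as a whole-group rate. On that reading there is no inflation. But neither document describes baseline thresholds in the source of the 20%, so the question stays open.
- **The planned outputs already show these children.** Largely true. Table 2.2 lists challenge results by patient, and Tables 2.3 and 4.3 summarise tolerated doses. What no planned output gives is the response rate and interval among children below 300 mg at baseline.

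A reader might infer from the second row of the first table that the type I error is inflated to 8.6% or more. The documents do not support that: those mixes lie outside the null, and they need certain passing and a 20% rate that excludes such children. Certain passing is itself an extreme, since non-completers count as non-responders. A reader might also take a subset bound at or below 20% after a successful primary test as evidence against the primary result. It is not; with 7 to 9 children it may simply be a miss of a real effect.

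**Conclusion.** The point holds at low severity. The endpoint and entry rules together allow a child to count as successfully desensitized with no rise in threshold, and from a baseline of 1000 mg no rise could be demonstrated. The exact test, its 3.3% size and its power stand. Only the interpretive step to desensitization beyond placebo is weakened.

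The size depends on two things that the documents do not give: k, and whether the 20% already covers such children. It runs from no effect to the upper figures in the working. For k up to 3, the practical consequence is confined to totals of 5/10 or 6/10. If no such child enrolled, or if at least seven of ten respond, the reading against 20% is unchanged.

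**What to change.** Keep the primary endpoint, population and test. Make these changes to the SAP:

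1. **Section 10.1, new paragraph.** *Supportive analysis, without a hypothesis test: the response rate with a two-sided 90% Clopper-Pearson interval will be given among ITT children whose highest tolerated dose at the initial OFC was below 300 mg (100 mg or less on that ladder). Non-completers count as non-responders. The desensitization conclusion will be interpreted in light of this estimate, which is not a second criterion for success.*
2. **Table 2.1.** Report beside it the number of children at 500 or 1000 mg at baseline. Add a footnote that children who tolerated 100 mg and reacted at 500 mg were never tested at 300 mg at baseline. They stay in the subset, so some ambiguity remains.
3. **Section 8.3.** Amend to: *No subgroup analyses are planned other than the supportive analysis in section 10.1.*

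The cost is one paragraph, one table row, one footnote and one amended sentence. The data are already on the initial challenge form.

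The downside is a smaller n and a wider interval. The subset needs 5/9, 5/8 or 4/7 for its bound to exceed 20%. At a true response of 50% that happens 50%, 36% and 50% of the time; at the planned 80%, 98.0%, 94.4% and 96.7%. The report should therefore say that an interval reaching below 20% does not show absence of effect.
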